and the Sponsor that would prevent dose escalation (also documented through e-mail communication), we will commence enrollment of the 12 participants in the next dose group (200mg qD arm). We will again conduct a safety review of adverse events via e-mail after the first 6 participants in the group complete day 42 followup while continuing with the next 6 participants in the group as above, following the same procedures before starting the 400mg imatinib group. After 6 participants complete day 42 followup in the 400 mg qD arm, we will review safety data and PK/PD data while enrollment in the 400 mg/day group continues. If the safety criteria above are met, we will complete enrollment of remaining participants in the 400 mg qD arm. This approach will proceed until there are 12 participants with evaluable myelopoiesis data in each dose arm and the sample size of 48 participants (16 in the previous protocol version plus 32 in this version) is fulfilled. All enrolled participants will be evaluable for safety and toxicity assessments if they have taken at least one dose of a study drug. Note that in this protocol version, given imatinib dosing only occurs for 28 days, 42-day followup is required for a participant to “count” toward the 6 needed for followup assessment. Therefore, if any of the first 6 participants in a dose group do not complete the study to day 42, we will need to include other participants who complete the day 42 visit to fulfill the requirement. Similarly, because study endpoints require data collection up to day 14, if a participant drops out prior to day 14, we will enroll another participant to complete the required complement of 12 participants with protocol-compliant evaluable data (has taken $\geq 85\%$ of all doses of study drugs and completed visits to day 14) per dose group (see [Section 8.1](#) and [Section 8.2](#)).

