5.9 Participant Compliance Monitoring

Participant compliance will be assessed by observing therapy on study visit days and by participant self-report and pill count during intervals between visits. Adherence will be tracked by noting whether the participant received/took the correct dose of the product using the above methods. The protocol adherence for each participant can be quantified for the 28-day dosing period using pill counts, using the formula #doses taken divided by number of prescribed days for an interval, x 100 (to get a percent adherence). Acceptable protocol-compliance is defined as taking $\geq 85\%$ of all doses of study drugs and completed visits to day 28. All participants taking at least one dose of the study drug and who do not withdraw consent will be followed for the full 42-day period.

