6.4 Participant Withdrawal and Discontinuation

Participants may withdraw from the study at any time without impact to their care. They may also be discontinued from the study at the discretion of the Investigator. Specific criteria for Permanent and Premature Treatment Discontinuation include the following:

- Positive SARS-CoV-2 antigen or PCR test
- Any documented serious viral or bacterial infection (COVID-19, influenza, cytomegalovirus, adenovirus, strep throat, etc.)
- Any infection that requires treatment or is associated with significant symptoms (fever, shortness of breath, muscle aches, headache)
- Failure by the participant to attend 3 consecutive study visits and/or failure to comply with 2 or more doses of study drugs
- Protocol-defined drug-related toxicity of grade 3 or higher
- Requirement for prohibited concomitant medications
- Pregnancy or breast-feeding
- Request by participant to terminate treatment
- Clinical reasons believed life threatening by the physician, even if not addressed in the toxicity section of the protocol

It will be documented whether or not each participant completes the clinical study. Participants who withdraw early, if willing, will have one final visit to collect investigational product and to follow up regarding adverse events. Participants may also be discontinued from the study for the following reasons:

- Request by the participant to withdraw
- Request of the primary care provider if she or he thinks the study is no longer in the best interest of the participant
- Participant judged by the investigator to be at significant risk of failing to comply with the provisions of the protocol as to cause harm to self or seriously interfere with the validity of the study results
- At the discretion of the study supporter (NIH/NIAID/DAIDS), the IRB/Ethics Committee, Food and Drug Administration (FDA), Office for Human Research Protections (OHRP), or other government agencies.

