8.1.2 Interim Analysis

Given imatinib is an FDA-approved drug with a known safety profile, we expect the doses used in this study to be well tolerated. After the first 6 participants in the 200mg dose group have completed the day 28 follow-up visit, the study team, the Data Safety Monitoring Board (DSMB),

the Independent Safety Monitor, and the Sponsor will evaluate the safety data and determine via email whether it is safe to proceed to enrolling in the 400mg dose group after the previous group is fully enrolled. Note that since 42-day follow-up is required for a participant that “counts” toward the 6 needed for follow-up safety analysis, if any of the first 6 participants in a dose group do not complete the study to day 42, we will need to include other participants who complete the day 42 visit in order to fulfill the requirement.

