9.5 Medical Monitoring and Toxicity Management

[name] is a Professor of Hematology and Oncology with extensive experience administering imatinib to CML patients at Emory University Hospital. She is certified by the American Board of Internal Medicine in Hematology. She will serve as the Independent Safety Monitor (ISM) for this study. [name] role will be to help monitor the safety of participants and adjudicate adverse events that may be related to imatinib. She has 9 years of experience as principal and co-investigator on multi-institutional clinical trials including trials evaluating transplantation for adults with acute leukemia. These collaborations have led to peer reviewed publications in high impact journals, such as *The Journal of Clinical Oncology*, *Cancer*, and *Lancet Oncology*. Her strong background in clinical investigation and experience as member, and now as vice chair of the Winship Data and Safety Monitoring Committee, make her exceptionally qualified to serve as the Independent Safety Monitor for the trial. The monitor will attest to the absence of relevant conflicts of interest as defined by NIAID and will be approved by all relevant regulatory bodies prior to beginning the study.

The ISM and the PI/co-PI will review safety data as enrollment progresses, assessing AE summaries in real-time and formally on a weekly basis for clinical significance and facilitating attribution to study medication (protocol [Section 9.2](#) and [Section 9.3](#)). The ISM will provide information to the DSMB on frequency and severity of AEs.

For individual toxicity management, the PI will review all toxicity reports of grade 2 or higher in real time in order to decide on possible need for intervention or drug discontinuation. In general, a grade 2 AE thought to be related to a study drug that does not respond to non-pharmacologic intervention (e.g., salt restriction and elevation of legs for pedal edema) will lead to consideration for drug discontinuation, and any grade 3 or higher AE will cause discontinuation of study drug. Participants taken off study drug will be followed for safety if willing but will not participate in PK studies.

For manual differential ALC and ANC lab values classified as Grade 3 - Grade 4 AEs, the study team will request that the Emory Medical Lab re-check the counts using the same specimen.

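### Day-42 follow-up alone, with no minimum exposure, decides who counts toward the six-person escalation look, so one early non-toxic stop can take it slightly below its stated 90% detection

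*Combined protocol and SAP*

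**What the plan says.** All references are to Version 5.0 in the combined document.

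- **Who counts.** Section 3.1.2: "Note that in this protocol version, given imatinib dosing only occurs for 28 days, 42-day followup is required for a participant to" count toward the six. Replacement depends on the same condition: "if any of the first 6 participants in a dose group do not complete the study to day 42, we will need to include" others who do reach that visit. The 85%-of-doses rule in the same section applies to the 12 participants evaluable for myelopoiesis, not to the six.
- **Interim analysis.** Section 8.1.2 starts the 200 mg review "After the first 6 participants in the 200mg dose group have completed the day 28 follow-up visit" but then repeats the day-42 condition ("Note that since 42-day follow-up is required for a participant that" counts). It sets no dose minimum either.
- **Early stops.** Section 6.4 ends treatment for, among other reasons, "failure to comply with 2 or more doses of study drugs", and for an infection that needs treatment or causes significant symptoms.
- **Follow-up after stopping.** Section 5.9: "All participants taking at least one dose of the study drug and who do not withdraw consent will be followed for the full" 42 days. Section 9.5: "Participants taken off study drug will be followed for safety if willing but will not participate in PK studies".
- **Claimed performance.** Section 9.5.1 says six participants who completed day 42 give more than 90% power to detect a safety signal when the true rate of grade 3 or higher toxicity is 33% or more. Accrual at a dose halts for DSMB review on one related grade 3 or higher dose-limiting toxicity in any participant.
- **The 100 mg group.** Sections 3.1 and 3.1.2 form its six from four participants carried over from the earlier version plus two new ones. The preface says the earlier version gave imatinib alone for two weeks and then added rifabutin and isoniazid.

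**The concern.** The 90% claim treats each of the six as having been exposed to the full risk of the 28-day course. The counting rule secures follow-up but not exposure. A volunteer taken off drug early for a respiratory infection, or after missing two doses, who then attends day 42, fills a place while carrying only part of the risk. The look then has fewer than six informative members, and nothing in the text triggers a replacement.

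At stake is the stated operating characteristic of a look that helps to open a doubled dose in healthy volunteers. Myelopoiesis has an exposure floor; the safety look has none.

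**Working it through.** **Inputs from the documents.** Six participants, a 33% true rate, a signal defined as at least one event, and a claim of more than 90% (Section 9.5.1); 28 planned doses (Study Summary); 85% adherence over 28 days (Section 5.9).

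**Assumptions not in the documents.** The number of early stops in the six (taken as one), and how toxicity risk is spread over the 28 days.

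**Step 1: reproduce the plan's figure.** P(at least one event in six) = 1 − 0.67^6 = 0.9095, or 0.9122 if the rate is taken as 1/3. The claim is correct. Requiring two or more events would give only 0.642, so the rule is one or more.

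**Step 2: the slack.** Full-exposure equivalents needed for 90% = ln(0.1)/ln(0.67) = 5.75 of 6 (5.68 at a rate of 1/3).

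**Step 3: one member stops early, constant hazard.** With f the fraction of the 28 days taken, detection = 1 − 0.67^(5+f).

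| One member stops | f | Detection |
|---|---|---|
| with negligible risk | 0 | 0.865 |
| after 4 doses | 4/28 | 0.873 |
| at day 14 | 0.5 | 0.889 |
| at day 21 | 0.75 | 0.900 |

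Break-even is 0.75 × 28 = day 21, or 0.679 × 28 = day 19 at a rate of 1/3.

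**Step 4: toxicity that comes early.** If 80% of the risk falls in days 1 to 14, a day-14 stop gives 1 − 0.67^5.8 = 0.902, so there is no shortfall. Risk that comes late moves the result toward 0.865.

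**Step 5: what volunteers 7 to 12 add.** With one zero-risk member among the six, 5.75 − 5 = 0.75 equivalents are missing. Six further volunteers supply that with 0.75/6 × 28 = 3.5 dosing days each. If all six were fully exposed, detection would be 1 − 0.67^11 = 0.988.

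**Step 6: the 100 mg look, for 28 days of imatinib alone.** Two new participants carry full weight; the four carried over have an assumed weight w, giving 1 − 0.67^(2+4w). This is 0.798 at w = 0.5, 0.875 at w = 0.8 and 0.910 at w = 1.

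**The case against.** The strongest case has four parts.

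**The route may not exist.** Section 6.2 says COVID-19 leads to study discontinuation as in Section 6.4, and Section 6.4 lists it beside the other triggers. If every trigger ended participation, these people would have a close-out visit, miss day 42 and be replaced. This stands for COVID-19. It does not carry over to the rest: the list in Section 6.4 is of reasons to stop treatment, and Section 5.9 follows to day 42 anyone who took one dose and has not withdrawn consent.

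**The six do not gate escalation alone.** Section 9.5.1 halts a dose for a related dose-limiting toxicity in any participant and sends the DSMB reports at the 6- and 12-participant points. Section 3.1.2 weighs safety concerns in volunteers 7 to 12, and Section 12.1 requires a DSMB recommendation before each new level. This largely stands. The limits are that Section 9.5.1 needs 12 enrolled, not 12 finished, and that it states its 90% for the six. A reader might infer that escalation is unprotected; the documents do not support that.

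**The loss is small.** Put as the toxicity rate detectable with 90% probability, one day-14 stop moves it from 1 − 0.1^(1/6) = 31.9% to 1 − 0.1^(1/5.5) = 34.2%, and a zero-risk member moves it to 1 − 0.1^(1/5) = 36.9%. This stands.

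**The carry-over is disclosed.** It is, and the 0.798 in Step 6 treats days 15 to 28 on the combination as giving no information. A reader might infer that the 100 mg look has only 80% power; that follows from an assumed weight, not from the documents.

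**Conclusion.** The gap is real and minor. The counting rule lets a volunteer who stopped drug early for a non-toxic reason fill one of the six places. If that happens once, before about day 19 to 21 under a constant hazard, the six-person look detects a 33% rate with probability of roughly 0.865 to 0.90 instead of 0.9095. The size rests on two assumptions, one such stop and the spread of risk over time; the documents give no early-stop rate.

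Two stronger readings should be resisted. The 90% figure itself is not wrong: it reproduces for six exposed people. Nor can poor adherers who stay on drug dilute the look to any degree, because two missed doses already end treatment under Section 6.4. Anyone properly kept on drug has missed at most 1 of 28, so the gap is confined to early stops.

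The 100 mg composition is a secondary note: four of its six had 14 days of imatinib alone, and the effect on the look cannot be fixed without assumed weights.

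**What to change.** In Sections 3.1.2 and 8.1.2, define the six as participants who either:

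- took at least 85% of the 28 planned doses (0.85 × 28 = 23.8, so 24) and reached day 42; or
- stopped drug or left because of an adverse event not clearly unrelated to study drug. These are kept and never replaced.

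Replace only members who were under-dosed for clearly unrelated reasons. Doubtful cases stay in, since an infection or missed doses may reflect intolerance. Adverse events in all dosed participants still go to the DSMB.

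The 85% figure comes from Section 5.9: "The protocol adherence for each participant can be quantified for the 28-day dosing period using pill counts". The text should say 28 planned doses explicitly, because the compliant population in Section 8.2 requires visits only to day 14. Twenty-one doses would be the bare break-even for one member; 24 keeps a margin (1 − 0.67^(5+24/28) = 0.904) and reuses a figure already in the plan. Two members at the floor would give 1 − 0.67^(4+48/28) = 0.899, a negligible shortfall.

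In the 100 mg review, add one sentence saying that the four carried-over participants contribute 14, not 28, days of imatinib-alone exposure.

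The cost is two or three sentences by amendment. The look may wait for another participant, normally already among the planned 12. Some judgement on attribution remains, which Section 9.3 gives to the principal investigator; keeping doubtful cases in limits its influence.

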3.1.3 Follow Up Phase

Participants will be followed for an additional 14 days after study drug administration. All participation in the study should be complete by day 50 after enrollment.

3.1.4 Allocation to Interventional Group

Imatinib dose allocation will occur in an ascending manner, with safety evaluations before proceeding to the next higher dose as described in [Section 3.1.2](#).

3.2 Study Endpoints

3.2.1 Primary Study Endpoints

- The primary endpoint is the change in the number of myelomonocytic cells in the blood between baseline and day 14 of imatinib (imatinib alone).
- The primary safety endpoint will be grade 3 or 4 events and SAEs. All AEs regardless of grade will be recorded and monitored. Safety will be primarily determined by the percent of participants on study who experience a grade 3 or 4 AE or a serious adverse event (SAE) that are considered related to the study drug. An SAE is defined as any untoward medical occurrence that meets any of the following criteria:
 - Results in death, or is life-threatening
 - Results in participant hospitalization or prolongation of existing hospitalization
 - Results in persistent or significant disability/incapacity
 - Is a congenital anomaly/birth defect

Other medically important conditions will also be assessed. These conditions include important medical events that may not be immediately life-threatening or result in death or hospitalization but may jeopardize the participant or may require intervention to prevent one of the outcomes listed in the definition above.

3.2.2 Secondary Study Endpoints

- Evaluation of the PK parameters.
- Additional research endpoints related to immunologic effects will include measures of cellular immune function and biomarkers of immune activation circulating in blood and expressed on the surface of T cells and monocytes.
- Secondary efficacy analyses will determine 1) the difference between the change in the numbers of myelomonocytic cells from baseline to day 14; 2) the relationship between imatinib exposures and change in the numbers of myelomonocytic cells during the imatinib-exposed periods; and 3) the relationship between imatinib dose and blood levels and the BCG-killing activity of day 14 leukocytes in the WBA .
- Finally, as exploratory analyses, we will evaluate the proteomic and transcriptomic changes associated with imatinib.

4 Study Population and Duration of Participation

4.1 Inclusion Criteria

- Adult age \geq 18 years & \leq 55 years
- Body mass index (BMI) $>18.5 \text{ kg/m}^2$
- At least 8 years formal education, with appropriate reading and comprehension skills
- Able and willing to provide written informed consent
- Males must agree to using contraception during the study and for 2 weeks after the last dose of study drug.
- If a female participant is of reproductive potential, the participant (and her partner) must agree to use of one of the following combinations of birth control during the study and for 2 weeks after the last dose of study drug (or tubal ligation as a single method):
 - 1) Use of a double-barrier method of contraception: condoms (male or female) and a diaphragm or cervical cap with spermicide;
 - 2) Use of an IUD (hormonal or non-hormonal) and a barrier method: condoms (male or female, with or without spermicide) or a diaphragm or cervical cap with spermicide;

3) Use of hormone-based contraceptives (pill, patch, implant, ring, or injectable) and a barrier method: condoms (male or female, with or without spermicide) or a diaphragm or cervical cap with spermicide;

4) Tubal ligation.

Women who are post-menopausal, defined as age greater than 45 and no menses for at least 1 year, or who have had a hysterectomy, are considered not of reproductive potential.

4.2 Exclusion Criteria

- Current or imminent treatment for significant infection
- Pregnant or breastfeeding
- HIV positive status as determined by an FDA-approved HIV assay
- Hepatitis B infection, as determined by an FDA-approved hepatitis B surface antigen assay
- Hepatitis C infection, as determined by an FDA-approved positive Hepatitis C antibody assay
- Known infection with Mycobacterium tuberculosis (MTB)
- History of allergy or hypersensitivity to imatinib.
- History of enrollment in other clinical trials with investigational agents within 8 weeks
- Cardiac arrhythmia requiring medication, or any clinically significant ECG abnormality
- Exam consistent with congestive heart failure (e.g., edema)
- Random blood glucose >140 mg/dL or history of unstable diabetes mellitus requiring hospitalization for hyper or hypoglycemia within the past year prior to start of screening
- Use of systemic corticosteroids within the past 28 days
- Any of the following readings from a complete blood count that fall outside the normal ranges as listed here:

White blood cell count: 3.4 10E3/mcL – 11 10E3/mcL

Hemoglobin: Female- 11.1 – 16.7 gm/dL, Male- 12.5 – 16.5 gm/dL

Platelet count: 150-400 10E3/mcL

Absolute neutrophil count: Female- 0.91-5.53 10E3/mcL, Male- 0.67-6.41 10E3/mcL

Absolute lymphocyte count: Female- 0.65-3.05 10E3/mcL, Male- 0.72-3.29 10E3/mcL

- Any of the following chemistry panel and liver function test readings that fall outside the normal ranges as listed here:

Serum potassium: 3.5-5.4 mmol/L

ALP: 34 – 104 unit/L

ALT: 4 - 52 unit/L

AST: 13 - 39 unit/L

Total Bilirubin: 0.2 - 1.0 mg/dL

Creatinine: Female- 0.60-1.32 mg/dL, Male- 0.7-1.3 mg/dL

- Cirrhosis of the liver, or any known active or chronic liver disease
- Current or past alcohol or illicit/recreational drug use, which in the expert judgment of the Investigator, will interfere with the participant's ability to comply with the protocol requirements.
- Any experimental medications for < 8 weeks prior to screening or anticipated use during the trial
- Current (within 30 days prior to the first dose of study drug) or anticipated use of antimetabolites; alkylating agents; or other drugs or herbal preparations (including St. John's wort), known to affect activity of the CYP3A4 enzyme pathway
- Consumption of grapefruit, grapefruit juice, or grapefruit-related citrus fruits (e.g., pomelos) within 7 days before assessment for eligibility
- Unwilling to avoid grapefruit or grapefruit-related citrus fruits/pomelo during the course of the study
- Unwilling to avoid alcohol for the duration of the study
- Unwilling to abstain from taking acetaminophen-containing medications during the 28-day study drug dosing period, due to increased risk of liver toxicity
- History of major medical disorders including metabolic, endocrine, hypothyroid, hepatic, renal, hematologic, pulmonary, gastrointestinal, autoimmune or cardiovascular disorders
- Uncontrolled hypertension (persistent measurements at or above 150/100)
- Participants who are, in the opinion of the Investigator, unable to comply with the dosing schedule and protocol evaluations
- Diarrhea defined as \geq 4 stools per day
- Active involvement (by the participant or the participant's partner) in In Vitro Fertilization or another assisted reproductive technology procedure
- Emory students currently enrolled in a course taught by the PI or a Co-Investigator
- Emory employees currently working under supervision of the PI or a Co-Investigator

